7.0 RECRUITMENT PLAN

This study will be available to all patients seen at Memorial Sloan Kettering Cancer Center and multicenter sites, who meet the eligibility criteria outlined in Section 6.0.

MSK is a large referral center for breast cancer in general and TNBC in particular. The Department of Radiation Oncology treats 900 new breast cancer patients across the network with post-lumpectomy or post-mastectomy RT. Estimating approximately 20% of these are TNBC patients, and approximately 70% of these received neoadjuvant chemotherapy. The pathCR rates are approximately 20%. Based on these assumptions, we should have approximately 100 eligible patients annually. Assuming a 15% participation rate, we should be able to complete the study in 2 years. [name] [name] will facilitate accrual across Radiation Oncology. The investigators take due

notice of the NIH policy concerning inclusion of women and minorities in clinical research populations. There will be no limitation to access with regard to race or gender. Patients will be required to read, agree to, and sign an IRB-approved informed consent form prior to registration on this trial. The registration procedure will be conducted as described in Section 15.0. Patients will not receive payment for their participation on this study.

8.0 PRETREATMENT EVALUATION

All baseline/screening procedures will take place after completion of surgery and within 30 days prior to initiation of protocol therapy, unless otherwise indicated.

- Signed informed consent
- Pathologic confirmation of TNBC or eligible hormone-receptor positive breast cancer
- History and physical examination including height, weight, vital signs (temperature, pulse rate, respiratory rate, blood pressure, pulse oximetry), performance status (ECOG), adverse event monitoring and review of medications
- 12-lead electrocardiogram (EKG)
- Serum pregnancy test for all women of childbearing potential
- CBC with differential and platelet count
- Complete metabolic panel (sodium, potassium, chloride, bicarbonate, BUN, creatinine, glucose, total protein, albumin, bilirubin, alkaline phosphatase, AST, ALT, corrected calcium, magnesium)
- Patient outcomes questionnaire (BCTOS), if applicable
- Patient and Physician Cosmesis evaluations
- Digital Breast Images
- If germline BRCA status is not known at the time of study registration, patients will be referred to their respective Genetics department for evaluation of germline BRCA status and other genes, at the discretion of the treating physician and consulting geneticists.

9.0 TREATMENT/INTERVENTION PLAN

9.1 Rucaparib Administration

Rucaparib will be administered concurrently with radiotherapy, commencing on the evening following the first radiation treatment, and then twice daily throughout the standardized 6-week course of radiation treatment to the breast with or without regional nodes. Subjects will receive rucaparib at their assigned dose level, beginning with dose level 0. Subjects will be instructed to take rucaparib as morning and evening doses, separated by approximately 12 hours, at the same time each day (BID dosing). Rucaparib treatment will be continued throughout the course of RT, including weekends or holidays when radiation fractions may not be administered. Rucaparib administration will continue for four weeks after the final fraction of RT.

Treatment will be administered on an outpatient basis. Subjects will receive sufficient quantities of capsules of rucaparib for administration every 2 weeks over the study duration. Subjects will be provided self-administration instructions and subject drug diaries to record the date and time study drug was taken. Subjects will be instructed to store study drug according to the label, subjects should return all study drug bottles and their drug diaries at their study visits.

Daily oral rucaparib should be taken with a glass of water, with or without a meal. Tablets should be swallowed whole without crushing or chewing. In case of vomiting after a dose of rucaparib, the dose should not be re-administered. If a patient misses a dose and less than 4 hours have passed since the scheduled dose time, the dose should be immediately taken. If more than 4 hours have passed since the scheduled time, the subject should not take the missed dose and wait to take the next scheduled dose.

9.2 Radiation Treatment

RT will be performed using external beam ionizing radiation in accordance with standard practice. The dose of radiation will be a standard regimen/fractionation used after neoadjuvant chemotherapy and breast conserving surgery/mastectomy: 50 Gy, delivered in twenty-five 2 Gy fractions over 5 weeks. In lumpectomy patients, a 10 Gy boost, delivered in five 2 Gy fractions over one week to the lumpectomy cavity is mandatory. In mastectomy patients, a 10 Gy boost delivered in five 2 Gy fractions over one week to the mastectomy scar is optional. The total prescribed dose will be 60 Gy in thirty 2 Gy fraction sizes for lumpectomy patients, and 50-60 Gy for mastectomy patients

. Conformance with dose parameters and constraints as specified in RTOG1304/NSABP-B51 is strongly suggested but not required.

The study can be found at: <https://www.ctsu.org/Master/SimplePage.aspx?ascx=ProtocolsReport>

RT will be administered using megavoltage linear accelerators once daily, 5 days per week (excluding weeks that include holidays, where the number of treatment days will be at the treating physician's discretion).

Details on radiation treatment, including the radiation consultation note, treatment plan, and treatment summary will be collected.

9.3 Research Biopsy

Tumor tissue will be collected from the diagnostic and the lumpectomy specimens, if available, precluding the need for an extraneous biopsy. Tissue analyses are detailed in Section 10.0.

9.4 Subsequent Therapies

Initiation of systemic therapy after completion of protocol treatment is at the discretion of the treating investigator, but should be delayed until no earlier than 30 days following completion to allow for assessment of acute toxicity and to allow full recovery for the sequelae of study treatment, unless such a delay would be harmful to the subject. Specifically, treatment with adjuvant capecitabine and/or pembrolizumab is allowed at the discretion of the treating physicians. Adjuvant endocrine therapy is allowed at the discretion of the treating physician and can be started before, during, or after protocol therapy.

Additional surgery is also at the discretion of the treating investigator but is not recommended for 30 days following the last RT session to allow evaluation of DLT and resolution of acute toxicity during that period. However, if delaying a surgical procedure would be harmful to the subject, surgery is allowed at the discretion of the treating investigator.

9.5 Definition of Dose-Limiting Toxicity

Dose-limiting toxicity (DLT) will be defined as toxicities probably or definitely related to the study drug observed during the 70 days that include 6 weeks of radiotherapy and 4 weeks of maintenance rucaparib therapy, as follows:

- Confluent moist desquamation, defined as the presence of a single, contiguous region of moist desquamation that exceeds 25 cm² in area
- Absolute Neutrophil Count <1,000/mm³, with or without fever
- Platelet count <50,000/mm³
- Hemoglobin <8.0 g/dl
- Any ≥ Grade 3 non-hematologic toxicity by the NCI CTCAE version 4.03, not including Grade 3 ALT/AST elevation provided bilirubin and alkaline phosphatase meet criteria in Section 11.2
- Any toxicity requiring a RT dose delay exceeding 5 business days

Toxicities meeting this definition and occurring during the observation period of 10 weeks (70 days) will influence the dose level assignment of the TITE-CRM algorithm if these toxicities are deemed probably or likely related to study therapy.

Sites should contact the coordinating center as soon as possible (within one business day) when a DLT occurs or seems imminent. Sites should call [name] [name], and send an email to [name] [name] and study coordinator.

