11.2 Dose Modifications

Radiation therapy may be withheld due to acute toxicity at the discretion of the treating investigator without being considered a dose-limiting toxicity if the treatment break is no greater than 5 days. All radiation treatment breaks should be recorded, including details regarding duration of break and reason.

Rucaparib dose will not be modified on this study. Treatment with rucaparib should be held if any of the following are observed:

Table 11B

Toxicity	Rucaparib Treatment Action	Timing for Restarting Rucaparib Treatment
----------	----------------------------	-------------------------------------------

Confluent moist desquamation (single, contiguous region of moist desquamation that exceeds 25cm ² in area)	Record DLT	Discontinue rucaparib
Any toxicity requiring a radiotherapy dose delay exceeding 5 business days	Record DLT	Discontinue rucaparib
Grade 3 or 4 hematologic toxicity Includes defined DLTs: Absolute Neutrophil count <1,000/mm ³ (with or without fever) Platelet count <50,000/mm ³ Hemoglobin <8.0 g/dl	Record DLT	Discontinue rucaparib
Grade 3 or 4 non-hematologic toxicity Except for: 
• alopecia, nausea, vomiting, or diarrhea adequately controlled with systemic antiemetic/antidiarrheal medication administered in standard doses according to the study center routines• Grade 3 ALT/AST elevation (see below)	Record DLT	Discontinue rucaparib
Grade 4 ALT/AST elevations	Hold rucaparib	Restart treatment when values have returned to ≤ Grade 2. Monitor liver function tests weekly for 3 weeks after reintroduction of rucaparib. Any toxicity requiring a radiotherapy dose delay exceeding 5 business days should be recorded as a DLT and rucaparib discontinued.

Grade 3 ALT/AST elevations	Continuation of rucaparib with elevation of ALT/AST up to Grade 3 is permitted provided: 
• bilirubin is < ULN• alkaline phosphatase is < 3x ULNand• there are no other signs of liver dysfunction	Monitor liver function tests weekly until resolution to ≤ Grade 2. If patient has Grade 3 ALT/AST and continues on rucaparib, and levels do not decline within 2 weeks or they continue to rise, treatment interruption and resolution to ≤ Grade 2 will be required before rucaparib can be resumed at current dose.

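### Table 11B conflicts with the governing DLT definition in Section 9.5: it drops controlled Grade 3–4 nausea, vomiting and diarrhea from DLT recording, and it gives two incompatible drug actions for Grade 4 ALT/AST

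*Combined protocol and SAP*

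**What the plan says.** Sections 1.0 and 14.0 both send the reader to Section 9.5 for the DLT definition. For non-hematologic events probably or definitely related to study drug within 70 days, Section 9.5 counts "Any ≥ Grade 3 non-hematologic toxicity by the NCI CTCAE version 4.03, not including Grade 3 ALT/AST elevation". The exemption holds provided bilirubin and alkaline phosphatase meet the Section 11.2 criteria. Events meeting the definition "will influence the dose level assignment of the TITE-CRM algorithm". On reporting, Section 9.5 adds: "Sites should contact the coordinating center as soon as possible (within one business day) when a DLT occurs or seems imminent".

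Table 11B in Section 11.2 has a row headed "Grade 3 or 4 non-hematologic toxicity Except for", whose action is to record a DLT and discontinue rucaparib. It has two exceptions. One is "alopecia, nausea, vomiting, or diarrhea adequately controlled with systemic antiemetic/antidiarrheal medication administered in standard doses". The other is Grade 3 ALT/AST elevation.

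A separate row for Grade 4 ALT/AST says to hold rucaparib, then "Restart treatment when values have returned to ≤ Grade 2" and "Monitor liver function tests weekly for 3 weeks after reintroduction of rucaparib". The text above the table says "Rucaparib dose will not be modified on this study".

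**The concern.** DLT status is the input to every dose assignment and to the MTD, which is the primary endpoint. Sites are given a definition in one section and a recording instruction in another, and the two differ on nausea, vomiting and diarrhea, all of which Table 11A lists among the principal rucaparib side effects. If a site works from the table, a patient with such a DLT stays in the TITE-CRM as a non-event, and under Section 14.0 her weight grows with follow-up until someone reclassifies her. Meanwhile up to 4 patients a calendar month may be enrolled.

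The liver-enzyme conflict is of another kind. One row takes a patient with Grade 4 ALT/AST off drug; the next rechallenges her. What is at stake there is her safety and consistent treatment across sites.

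**Working it through.** The plan states no figure on this point, so the check is a comparison of text.

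| Drug-related event within 70 days | Section 9.5 | Table 11B |
|---|---|---|
| Grade 3–4 nausea, vomiting or diarrhea, adequately controlled on standard-dose medication | DLT | Excepted from the row that records a DLT; no row of its own |
| Same event, not adequately controlled | DLT | Record DLT, discontinue |
| Grade 3 ALT/AST, bilirubin and alkaline phosphatase criteria met | Not a DLT | Continue and monitor |
| Grade 4 ALT/AST | DLT | General row: record DLT, discontinue. Separate row: hold, restart at Grade 2 or lower |

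**Does Section 9.5 import the gastrointestinal exception?** No. Its cross-reference to Section 11.2 covers bilirubin and alkaline phosphatase only. The first line of the table is a genuine mismatch.

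**Does Grade 4 ALT/AST escape the general row?** Not by its terms. That row excepts Grade 3 ALT/AST and is silent on Grade 4, so Grade 4 stays under record and discontinue. The separate row then calls for restart, and because the dose is never modified, restart is at the unchanged dose. Nothing says which row prevails. The separate row mentions a DLT for radiotherapy delays over 5 business days, but it does not say that this is the sole circumstance in which one is recorded. Section 9.5 therefore still makes the event a DLT.

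**Would a missed flag be caught?** Table 10B has all adverse events graded and entered whether or not they are DLTs. Section 16.0 has the PI confirm that the toxicity data are correct and current before each assignment. Neither says that events are to be re-judged against Section 9.5. Contact within one business day depends on the site recognising the DLT.

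**Patients covered.** As of 8/7/2019, 7 of 30 had been accrued, leaving 30 − 7 = 23. This counts patients to whom the wording applies.

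**Can one event matter?** An illustration on assumed data:
- Model: one-parameter logistic CRM with the revised expected probabilities in Section 14.0 (0.20, 0.30, 0.40, 0.50, 0.62, 0.70, 0.76).
- Assumed constants: intercept 3, normal prior with variance 1.34, all patients fully followed.
- Assumed data: 1/2 DLTs at level 0 and 2/5 at level −1.

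| Further patients, assumed | Cap for next patient | DLTs among them → level assigned (estimate) |
|---|---|---|
| 6 at level −3 (7 + 6 = 13 treated) | 35% | 1 → −2 (0.29); 2 → −3 (0.29); 3 → −4 (0.30); 4 → none admissible |
| 10 at level −3 (7 + 10 = 17 treated) | 30% | 2 → −3 (0.21); 3 → −3 (0.28) |

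Across all the assumed cases run, under both caps and with an empiric model as well, reclassifying one event moved the assignment by 0 or 1 level or left no admissible level. This shows that a single event can matter. It does not estimate a bias, because neither the counts nor the model constants are in the documents.

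**The case against.** The strongest reply is that the endpoint is not ambiguous. Sections 1.0, 9.5 and 14.0 make Section 9.5 the definition. Table 11B sits under dose modification, states neither the attribution requirement nor the 70-day window, and in its hematologic row refers to DLTs as already defined. That stands: Section 9.5 governs. But the table's action column tells sites to record a DLT, so it is a recording instruction as well as a drug-management one, and Section 7.0 makes this a multicenter study.

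It can also be said that central checks will catch the event, and that the discordant case is narrow: Grade 3 or higher, attributable, within the window, and controlled on standard-dose medication. Both points lower the risk. Table 11A gives no grades or frequencies, so the documents do not show such events to be common. The checks nonetheless lack an express step for re-judging against Section 9.5.

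On liver enzymes, the specific row might be read as overriding the general one. The plan does not say so, and that reading would mean rechallenge after a DLT, whereas every row that records a DLT unconditionally also discontinues the drug.

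A reader might go further and infer that the TITE-CRM is running on the wrong definition, that the MTD is biased, or that Table 11B makes Grade 4 ALT/AST a non-DLT. The documents support none of these. Section 9.5 feeds the algorithm, no discordant event is documented, and the Grade 4 row does not remove the event from the definition.

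**Conclusion.** The inconsistency is real and should be fixed, on two separate grounds. For controlled Grade 3–4 nausea, vomiting or diarrhea, the risk is that a Section 9.5 DLT is missed or flagged late, partly offset by central capture and the PI check. For Grade 4 ALT/AST, the problem is two drug instructions that cannot both be followed; it concerns treatment safety and should not borrow weight from the MTD.

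The effect on the MTD cannot be determined: the documents give no DLT counts or types. The figure of 23 patients still to accrue measures coverage of the wording and should not be read as a number misclassified. The conclusion rests on the current text of Sections 9.5 and 11.2 and on no model result.

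**What to change.** Align Table 11B to Section 9.5 and leave Section 9.5 as it is.

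- State in Section 11.2 that Section 9.5 alone defines DLTs. This also settles the hematologic row, whose heading is broader than the blood-count thresholds in Section 9.5.
- Remove the exemption for alopecia and controlled nausea, vomiting or diarrhea from the action that records a DLT.
- Give Grade 4 ALT/AST one action, record DLT and discontinue rucaparib, and delete the hold-and-restart row.
- Check the recorded Grade 3 or higher non-hematologic events of all treated patients against Section 9.5 before the next TITE-CRM run and before the final MTD estimate.

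Do not resolve the conflict by adding exemptions to Section 9.5. That would change the definition behind the primary endpoint mid-trial, after the expected toxicity rates were revised using accrued data.

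The cost is amendment wording in Section 11.2 and a review of events already in the database, with no change to design, sample size or assessments. The downside is clinical: a few patients with controlled Grade 3–4 gastrointestinal events, or with Grade 4 ALT/AST that has recovered, would come off rucaparib. The documents do not say how many.

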9.6 Concomitant Treatment and Supportive Care Guidelines

Prior and subsequent systemic therapy is allowed, with a 2-week washout required for all anti-cancer agents, including cytotoxic chemotherapeutic agents, immunotherapy, biologic therapy, and targeted therapies. There are no limitations on the type or number of prior regimens.

Bisphosphonates are permitted without restriction even during protocol treatment.

No surgery is to be performed while the patient is receiving protocol therapy. At least three weeks must elapse since completion of surgery before initiation of protocol therapy.

Any medication or vaccine including over-the-counter and prescription medicines, vitamins, and herbal supplements that the subject is receiving at screening up to the week 10 visit should be recorded in source documents and case report forms. Administration dates (start and end dates), dose, and frequency will be recorded. Any change in concomitant therapy during the study period will be recorded.

Subjects should receive the best supportive care and treatment during the study as appropriate, including transfusion of blood and blood products, oxygen therapy, nutritional support, intravenous fluids, and treatment with appropriate medications (antibiotics, antiemetics, antidiarrheals, and analgesics, etc.).

Questions regarding prior or concomitant therapy should be directed to the Principal Investigators.

9.6.1 Hematopoietic Growth Factors and Blood Products

Erythropoietin, darbepoetin alfa, and/or hematopoietic colony-stimulating factors for treatment of cytopenias should be administered according to institutional guidelines.

<https://one.mskcc.org/sites/pub/pharmacy/guidelines/IVMedGuide/IVMedGuidelines.pdf>

Transfusion thresholds for blood product support will be in accordance with institutional guidelines.

9.6.2 CYP450 Isoenzyme Inhibitors, Inducers, and Substrates

Based on results of in vitro CYP interaction studies, caution should be used for concomitant medications with narrow therapeutic windows that are substrates of CYP2C19, CYP2C9, and/or CYP3A. Selection of an alternative concomitant medication is recommended.

Table 4A. Examples of CYP Substrates with Narrow Therapeutic Range

CYP Enzyme	Substrates with Narrow Therapeutic Range ^a
CYP2C9	Warfarin, phenytoin
CYP2C19	S-mephentytoin
CYP3A	Alfentanil, astemizole, cisapride, cyclosporine, dihydroergotamine, ergotamine, fentanyl, pimozide, quinidine, sirolimus, tacrolimus, terfenadine

The table is based on US Department of Health and Human Services, Food and Drug Administration, CDER. Draft Guidance for Industry: Drug Interaction Studies - Study Design, Data Analysis, Implications for Dosing, and Labeling Recommendations. February 2012; Available from <http://www.fda.gov/downloads/drugs/guidancecomplianceregulatoryinformation/guidances/ucm292362.pdf>.

a. CYP substrates with narrow therapeutic range refers to drugs whose exposure-response relationship indicates that small increases in their exposure levels by the concomitant use of CYP inhibitors may lead to serious safety concerns (e.g., Torsades de Pointes).

9.6.3 Anticoagulants

Caution should be exercised in patients receiving rucaparib and concomitant warfarin (Coumadin) as rucaparib showed a mixed inhibition of CYP2C9 in vitro. If appropriate, low molecular weight heparin should be considered as an alternative treatment. Patients taking warfarin should have international normalized ratio (INR) monitored regularly per standard clinical practice.

9.6.4 Other Concomitant Medications

Therapies considered necessary for the patient's well-being may be given at the discretion of the investigator. Other concomitant medications, except for analgesics, chronic treatments for concomitant medical conditions, or agents required for life-threatening medical problems, should be avoided. Herbal and complementary therapies should not be encouraged because of unknown side effects and potential drug interactions.

In vitro data showed that rucaparib is an inhibitor of P-gp and thus patients taking digoxin, a P-gp substrate, should have their digoxin levels monitored regularly via standard clinical practice. Caution should also be exercised for concomitant use of certain statin drugs (e.g., rosuvastatin and fluvastatin) due to potential increase in exposure from inhibition of BCRP and CYP2C9.

9.7 Study Duration

Treatment is expected to continue for a total of ten weeks (70 days), as described, unless delayed by adverse events, or discontinued due to meeting criteria described in Section 13.1

Following the ten week course of study treatment, follow up visits will continue every 3-6 months for two years, or as per standard follow-up care. Participants removed from study for unacceptable adverse events will be followed until resolution or stabilization of the adverse event.

